2.3. Final Analysis

Due to early termination of the study by sponsor for lack of efficacy based on the interim futility analysis results, the final analysis of the data will be performed after all enrolled subjects have finished their follow-up/early-termination visit after the last dose of study drug, outstanding data queries have been resolved or adjudicated as unresolvable, and data have been cleaned and finalized.

3. GENERAL CONSIDERATIONS FOR DATA ANALYSES

Analysis results will be presented using descriptive statistics. For categorical variables, the number and percentage of subjects in each category will be presented; for continuous variables, the number of subjects (n), mean, standard deviation (SD) or standard error (SE), median, first quartile (Q1), third quartile (Q3), minimum, and maximum will be presented. Time-to-event endpoints will be summarized using median and quartiles of the Kaplan-Meier (KM) estimates.

3.1. Analysis Sets

Analysis sets define which subjects are included in an analysis. The assignment of subjects to analysis sets will be done before the study is unblinded for analysis. A summary of the number and percentage of subjects in each analysis set will be provided by treatment group and in total as part of the subject disposition summary.

3.1.1. Intent-to-Treat (ITT) Analysis Set

The Intent-to-Treat (ITT) Analysis Set includes all subjects who were randomized into the study, and will be analyzed according to treatment randomized. This is the primary analysis set for all efficacy analyses and summaries of demographics and baseline characteristics, unless otherwise specified.

A subset of the ITT Analysis Set will be utilized for the interim futility analysis, which includes subjects who have been on study for 24 weeks or have discontinued the study before 24 weeks, or have achieved a response prior to reaching 24 weeks.

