1.3. Sample Size and Power

With 40 subjects per treatment group, there is 75% power to detect a 30% improvement in response rate at a 2-sided 0.05 significance level using Fisher’s exact test, assuming a placebo response rate of 50%. A total of 100 subjects (50 per treatment group) will be enrolled assuming a 20% dropout rate.

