2. TYPE OF PLANNED ANALYSIS

2.1. Data Monitoring Committee Analyses

An external multidisciplinary Data Monitoring Committee (DMC) will review the progress of the study and perform interim reviews of safety and efficacy data for futility in order to protect subject welfare and preserve study integrity. The DMC is to recommend to the sponsor whether the nature, frequency, and severity of adverse effects associated with study treatment warrant the early termination of the study in the best interests of the participants, whether the study should continue as planned, or whether the study should continue with modifications.

The DMC will meet at designated intervals every 5 month after the first 20 subjects have been on study for 8 weeks to review accumulated safety data. The DMC will also review 1 formal interim analysis for futility when approximately 50% of subjects have been on study for 24 weeks or have discontinued the study before 24 weeks, or have achieved a response prior to reaching 24 weeks.

The DMC's role and responsibilities and the scope of analysis to be provided to the DMC are detailed in a mutually agreed upon charter, which defines the DMC membership, meeting logistics, and meeting frequency.

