2.2. Interim Analysis

The DMC is primarily responsible for reviewing safety data. Efficacy data will be reviewed only during the formal interim futility analysis after approximately 50% of subjects have been on study for 24 weeks, or have discontinued the study before 24 weeks, or have achieved a response prior to reaching 24 weeks. A non-binding futility rule will be implemented which is based on the predictive probability of success.

The predictive probability of success is defined as the probability of achieving statistical significance (two sided p-value < 0.05) and a $\geq 30\%$ difference in the BORR between the ENTO and placebo group at the study completion given the data observed at the interim.

If the predictive probability of success is $> 30\%$, the study will continue. If the predictive probability of success is $\leq 30\%$, the totality of the data including the DOR, response rate at Week 24, and safety data will be reviewed by the DMC to make a thorough risk-benefit assessment. The VP of Clinical Research and the VP of Biometrics at Gilead may review the interim futility analysis results to make subsequent decisions based on the DMC recommendations.

A 2-sided alpha of 0.001 will be allocated to this interim futility analysis; following the Haybittle-Peto approach, the week 24 analysis alpha level will be 0.05 (2-sided).

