Appendix 5. Predictive Probability of Success Calculation

Notation

Let

- n_1 =number of patients in treatment group
- n_0 =number of patients in control group
- n_{i1} =number of patients who stayed in trial at least 24 weeks or who stayed less than 24 weeks but responded already at interim in treatment group
- n_{i0} =number of patients who stayed in trial at least 24 weeks or who stayed less than 24 weeks but responded already at interim in control group
- n_{i11} =number of responders at interim in treatment group
- n_{i01} =number of responders at interim in control group
- x_1 =number of new responders after interim and at week 24 analysis in treatment group
- x_0 =number of new responders after interim and at week 24 analysis in control group

Predictive probability of success

Predictive probability of success is defined as the probability of obtaining a statistically significant 30% difference favorable result at the week 24 analysis (at 2-sided alpha level α), accounting for uncertainty about the true treatment effect given the data observed at the interim, and assuming that future data is subject to sampling variation given any possible true effect.

Predictive probability of success can be calculated as:

$$\sum_{x_1=0}^{n_1-n_{i1}} \sum_{x_0=0}^{n_0-n_{i0}} \left(\frac{n_{i11}+x_1}{n_1} > \left(\frac{n_{i01}+x_0}{n_0} + 0.3 \right) \right) \{pvalue(x_1, x_0) < 0.05\} f(n_1 - n_{i1}, x_1, n_{i11} + 1, n_{i1} - n_{i11} + 1) f(n_0 - n_{i0}, x_0, n_{i01} + 1, n_{i0} - n_{i01} + 1)$$

where function f is the probability density function of Beta-Binomial Distribution

$$f(n, x, a, b) = \binom{n}{x} \frac{\Gamma(x+a)\Gamma(n-x+b)}{\Gamma(n+a+b)} \frac{\Gamma(a+b)}{\Gamma(a)\Gamma(b)} \text{ where } \Gamma \text{ is gamma function.}$$

For Programming

```
/* **** */
/* Predictive probability of success Macro:
*/
/* Calculates the probability of statistical significance at final      */
/* analysis given data observed at interim                          */
/* **** */
/* Input Parameters:                                               */
/* n1 = sample size in treatment group                             */
/* n0 = sample size in control group                               */
/* ni1 = sample size stayed at least 24 weeks or less than 24 weeks but */
/*      responded at interim in treatment group                   */
/* ni0 = sample size stayed at least 24 weeks or less than 24 weeks but */

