/*      responded at interim in control group                     */
/* ni11 = responders at interim in treatment group                */
/* ni01 = responders at interim in control group                  */
/* alpha = 2-sided alpha level at week 24 analysis                */
/* **** */
```

```
%macro PP_calc(n1,n0,ni1,ni0,ni11,ni01,alpha);
```

```
proc iml;
n1=&n1; /*sample size in treatment group*/
n0=&n0; /*sample size in control group*/
ni1=&ni1; /*sample size stayed at least 24 weeks or less than 24 weeks but
responded at interim in treatment group*/
ni0=&ni0; /*sample size stayed at least 24 weeks or less than 24 weeks but
responded at interim in control group*/
ni11=&ni11; /*responders at interim in treatment group*/
ni01=&ni01; /*responders at interim in control group*/

c1=(n1-ni1); /*rest patients who are potential to have week 24 responses in
treatment group*/
a1=ni11+1;
b1=ni1-ni11+1;
c0=(n0-ni0); /*rest patients who are potential to have week 24 responses in
treatment group*/
a0=ni01+1;
b0=ni0-ni01+1;

pm=j(c1+1,c0+1,0);
fd=j(4*(c1+1)*(c0+1),4,0); /*data output for fisher's exact test*/
do x1=0 to c1;
    p1=comb(c1,x1)*beta(x1+a1,c1-x1+b1)/beta(a1,b1); /*the probability to
observe x1 more responders in treatment group*/
    do x0=0 to c0;
        pass=(x1*(c0+1)+x0)*4;

        p0=comb(c0,x0)*beta(x0+a0,c0-x0+b0)/beta(a0,b0); /*the probability to
observe x0 more responders in control group*/
```

```
        pm=p1*p0; /*the probability to observe x1 more responders in
treatment group and x0 more responders in control group*/
        fd[(pass+1):(pass+4),2]=repeat(pm,4,1);

        fd[(pass+1),1]=ni11+x1; /*count of treatment responses at final*/
        fd[(pass+2),1]=n1-ni11-x1; /*count of treatment non-responses at
final*/
        fd[(pass+3),1]=ni01+x0; /*count of control responses at final*/
        fd[(pass+4),1]=n0-ni01-x0; /*count of control non-responses at
final*/

        su=((ni11+x1)/n1>(ni01+x0)/n0+0.3); /*marker if treatment is superial
30%*/
        fd[(pass+1):(pass+4),3]=repeat(su,4,1);

        rn=x1*(c0+1)+x0+1; /*replicate number*/
        fd[(pass+1):(pass+4),4]=repeat(rn,4,1);
    end;
end;

indicator=repeat(t({1 1 0 0, 1 0 1 0}), (c1+1)*(c0+1), 1);

fm=fd||indicator;
varNames={"count" "pm" "su" "rep" "group" "response"};
create mydata from fm [colname=varNames];
append from fm;
close mydata;

quit;

proc sort data=mydata;
by rep;
run;
proc freq data=mydata;
by rep;
tables group*response/exact cmh;
weight count;

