ods output FishersExact=fx; /*output fisher's exact test result*/
run;
data fx1;
set fx;
if Name1='XP2_FISH';
keep rep Nvalue1;
run;

proc sort data=fx1;
by rep;
run;

data mydata1;
merge mydata fx1;
by rep;
if first.rep;
fp=(Nvalue1<&alpha)*pm*su; /*if the fisher's exact test is significant and
treatment is superial*/
```

```
drop count group response;  
run;
```

```
proc means data=mydata1 sum; /*add the probability together*/  
var fp;  
run;
```

```
%mend;
```

```
/* Sample macro call */
```

```
%PP_calc(n1=50,n0=50,ni1=25,ni0=25,ni11=20,ni01=10,alpha=0.05);
```

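### SAP 3.1.1 and Appendix 5 define the interim futility counts differently, and both let entry depend on outcome, so the predictive probability need not reflect BORR by 24 weeks

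*SAP*

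**What the plan says.** SAP 2.2 sets the timing of the futility look and SAP 3.1.1 its analysis set. Both use the same three routes of entry; in 3.1.1 the subset is those on study for "24 weeks or have discontinued the study before 24 weeks, or have achieved a response prior to reaching 24 weeks".

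SAP Appendix 5 gives the calculation. It defines the denominators ni1 and ni0 as the "number of patients who stayed in trial at least 24 weeks or who stayed less than 24 weeks but responded already at interim", which is two routes, with no mention of discontinuation. Everyone else in the arm falls into c1 = n1 − ni1 (c0 likewise), commented in the macro as "rest patients who are potential to have week 24 responses in" the group. The interim data give a posterior Beta(ni11 + 1, ni1 − ni11 + 1), which predicts the outcomes of all c1 remaining subjects. The sample call is "PP_calc(n1=50,n0=50,ni1=25,ni0=25,ni11=20,ni01=10,alpha=0.05".

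Under SAP 2.2, if the predictive probability of success (PPoS) is 30% or less, "the totality of the data including the DOR, response rate at Week 24, and safety data will be reviewed by the DMC". SAP 2.1 says "the scope of analysis to be provided to the DMC are detailed in a mutually agreed upon charter". SAP 1.3 allows for losses: "A total of 100 subjects (50 per treatment group) will be enrolled assuming a 20% dropout rate". Protocol 8.5.4 places the futility analysis on BORR by 24 weeks in the ITT set. SAP 2.3 begins "Due to early termination of the study by sponsor for lack of efficacy based on the interim futility analysis results".

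**The concern.** There are two linked problems.

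**Entry depends on outcome.** Before 24 weeks a subject is counted once he or she responds (both definitions) or leaves the study (3.1.1 only). An ongoing non-responder with equal follow-up is not counted. The early-responder route on its own raises the interim rate in each arm. Early entry of non-responding discontinuers pulls the other way and may offset this partly or fully. The resulting rate is then applied to everyone left out.

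**The two definitions disagree.** A non-responder who left the study is a known non-responder under 3.1.1. Read literally, Appendix 5 places the same subject in c1 with a predicted chance of responding, and the offset is lost. Only leaving the study matters here: under Protocol 6.5.2, subjects who stop study drug are asked to keep attending through Week 48.

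At stake is the number on which the futility review turned. Success requires a difference of about 30 points as well as p < 0.05, so a few points of distortion in the difference matter.

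**Working it through.** **1. The plan's own figures.** Exact enumeration of Fisher's test with 40 per arm, 50% v 80%, two-sided 0.05, gives power 0.749 (SAP 1.3 states 75%). Then 40/(1 − 0.20) = 50 per arm, 100 in total. Both agree with the SAP.

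**2. PPoS formula.** The beta-binomial sum of Appendix 5 was coded with n1 = n0 = 50, Fisher p < 0.05 and difference > 0.3 (the Appendix 5 coding; SAP 2.2 words it as at least 30%). The sample call, 20/25 v 10/25, gives 0.805. Double-precision evaluation of the comparison gives 0.810, because differences of exactly 30 points are then sometimes admitted.

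**3. Same data, two definitions** (ENTO, placebo). Take 16 and 10 responders, 4 and 10 non-responders at 24 weeks, and 5 and 5 discontinued non-responders.

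- SAP 3.1.1: denominators 16+4+5 = 25 and 10+10+5 = 25. Rates 64% v 40%, PPoS 0.205.
- Appendix 5: denominators 16+4 = 20 and 10+10 = 20. Rates 80% v 50%, PPoS 0.413.

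The two stay on opposite sides of 30% with double-precision comparison (0.227, 0.420) and with success coded as ≥ 30% (0.272, 0.486). The order can reverse: with 18 and 11 responders, 3 and 9 non-responders at 24 weeks, and 2 and 8 discontinued, 18/23 v 11/28 gives 0.776 and 18/21 v 11/20 gives 0.436.

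In the SAP's sample call the non-responders number 5 and 15. Leaving out 20, 40 or 60% of them as discontinued gives 20/24 v 10/22, 20/23 v 10/19 and 20/22 v 10/16, with PPoS 0.718, 0.578 and 0.367.

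**4. Early-responder rule alone.** Per arm, let m subjects be complete, k be in follow-up, p be the true rate and g the share of eventual responders in follow-up who have already responded. Then

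rate = (mp + kgp)/(m + kgp), inflation = kgp(1 − p)/(m + kgp).

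With m = 20, k = 10, g = 0.7 (assumed):

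- 80%: 21.6/25.6 = 84.4%; 50%: 13.5/23.5 = 57.4%. The difference falls from 30 to about 27 points.
- 60/30 becomes 66.9/36.7, almost unchanged.
- 40/10 becomes 47.4/13.0, so the difference widens.

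**5. Simulation.** Assumptions not in the documents: uniform accrual over 52, 78 or 104 weeks; first response at weeks 4, 8, 12, 16, 20, 24, either front-loaded (40/25/15/10/5/5% of responders) or even; dropout time uniform over 24 weeks; interim when 50 subjects qualify under 3.1.1. A flag is PPoS ≤ 30%. The comparator is a date set: 50 subjects, all randomised at least 24 weeks before the cut. There were 4,000 replicates per setting. Ranges run over the accrual lengths, with response 80/50 before dropout and front-loaded timing:

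| Dropout ENTO/placebo | True ITT difference | 3.1.1 difference (flags) | Appendix 5 difference (flags) | Date-set flags |
|---|---|---|---|---|
| none | 30 | 22.7–26.9 (51–65%) | same as 3.1.1 | 40–41% |
| 20/20% | 27.5–27.7 | 21.9–25.2 (56–64%) | 20.5–25.3 (56–71%) | 47–48% |
| 10/30% | 32.6–33.0 | 30.1–31.6 (36–41%) | 17.7–22.1 (64–77%) | 32–33% |
| 30/10% | 22.5–22.6 | 13.7–19.2 (71–85%) | 22.9–28.5 (46–65%) | 60–63% |

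With even timing and no dropout, the 3.1.1 difference is 25.4–27.8 (flags 47–55%). A separately coded simulation of that case, 3,000 trials per setting, gave 25.8, 27.6 and 28.4 points and flags of 54, 48 and 46%, against 38% for a complete cohort.

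Other settings, no dropout, 3.1.1 set:

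- 60/30: flags 38–41% v 39–40% for the date set.
- 40/10: 22–31% v 41–43%.
- 50/50: 97–98% v 97%.

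If 60% of non-responders leave within 12 weeks and timing is even, the 3.1.1 rates are 79.5–80.0% v 49.1–49.5%, so there is no upward bias. Appendix 5 then gives a difference of only 13.8–17.0 points (flags 79–87%).

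**The case against.** The strongest reply is that 3.1.1 is the operative text: it names the futility subset, and SAP 1.2, 2.1 and 2.2 list the same routes. Appendix 5 is notation plus a macro whose counts are typed in, so entering 3.1.1 counts removes the conflict. The sample call's 25 + 25 subjects fit the 50% trigger. That is fair, and the Appendix 5 results above apply only on a literal reading. The selection in 3.1.1 itself remains, and nothing in the readable text says which counts were entered. SAP 6.6, on changes from the protocol, is redacted and may address the departure from Protocol 8.5.4.

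The rule is also non-binding. A low PPoS leads to a review of all the data, and no formal comparisons remain after termination (SAP 3.5). This limits the consequence, but the DMC still needed a figure that estimates the stated endpoint.

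The sample-call variants never cross 30%, and their 60% case implies 3/25 v 9/25 discontinued, well away from a common 20%. That is correct; the crossing is shown by the 16 v 10 example. Accrual, timing and dropout patterns are assumed, and 60/30 and 40/10 are not planned scenarios. They are used only to show that the direction varies.

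**Conclusion.** The concern holds. The texts differ on non-responding discontinuers, and both make entry depend on outcome. At the planned 80/50 with similar timing in both arms and no dropout, the 3.1.1 set understates the difference by about 2 to 7 points and raises the flag rate from 40–41% to 47–65%. With success coded as ≥ 30%, the flags are 39–59% against 34–35%. With dropout, size and direction depend on its pattern and on which definition was entered. In some settings 3.1.1 does little harm.

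The 40–41% baseline flag rate comes from the required 30-point difference and is not part of this point. All rates rest on the stated accrual, timing and dropout assumptions. No interim counts are given, so it cannot be said that the definition changed the decision to stop.

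**What to change.** Use one definition in SAP 2.2, 3.1.1 and Appendix 5: all subjects randomised at least 24 weeks (plus the visit window) before the data cut, whatever their outcome. Within that set, subjects who left the study without a response count as non-responders in ni1 and ni0, never in c1 or c0. Everyone randomised later is treated as not yet observed.

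As the interim is past, the practical step is to state in the clinical study report which ni1 and ni0 were entered, re-run the PPoS once on the date-based set as a sensitivity analysis, and report both results.

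The cost is a few lines of text and one run on existing data. The trade-off is that some outcomes already known are set aside: about 24 to 43 subjects inform the posterior at the same cut instead of 50 (simulated 80/50 settings). In simulation at that cut, 80/50 is flagged in 38–41% of trials. An ineffective drug (50/50) is flagged in 93–96%, against 97–98% under 3.1.1. Used prospectively with 50 subjects, the interim would come about 6 to 13 weeks later.

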3.1.2. Safety Analysis Set

The Safety Analysis Set includes data from all subjects who received at least 1 dose of study drug, with treatment assignments designated according to actual treatment received. All data collected up to earlier of the last dose of study drug plus 30 days or first dose of OLE will be included in the safety summaries. The Safety Analysis Set will be used for analyses and summaries of exposure of study drug, corticosteroids, prior and concomitant medication, laboratory data, vital signs, and AEs.

3.1.3. Pharmacokinetics (PK) Analysis Set

The Pharmacokinetic (PK) Analysis Set will include all randomized subjects who took at least 1 dose of study drug and have at least 1 non-missing post-dose concentration value reported by the PK laboratory. This is the primary analysis set for all PK analyses.

3.2. Subject Grouping

For analyses based on the ITT Analysis Set, subjects will be grouped according to the treatment to which they were randomized. For analyses based on the Safety Analysis Set, subjects will be grouped according to the randomized treatment except when their actual treatment differs from randomized treatment for the entire treatment duration. In this case, subjects will be grouped based on actual treatment received.

For the PK Analysis Set, subjects will be grouped according to the actual treatment they received.

3.3. Strata and Covariates

Subjects will be randomly assigned to treatment groups via the interactive web response system (IWRS) in a 1:1 ratio using a stratified randomization schedule. Stratification will be based on the following factors:

- calcineurin inhibitor or mycophenolate mofetil (MMF) use (no vs. yes) at Screening
- moderate vs. severe cGVHD as determined by the NIH cGVHD Diagnosis and Staging Criteria (NCDSC) at the Screening

If there are discrepancies in stratification factor values between the IWRS and the clinical database, the baseline values recorded in the clinical database will be used for analyses. Both stratification factor values can be defined based on questionnaire data collected at the screening visit, and concomitant medicine data.

Efficacy endpoints will be evaluated using stratification factors as covariates or stratification variables for analyses.

3.4. Examination of Subject Subgroups

Due to early termination of the study by the sponsor, no pre-specified subgroup analyses for efficacy and safety will be conducted.

3.5. Multiple Comparisons

Due to early termination of the study by the sponsor, no formal statistical comparisons will be done.

3.6. Missing Data and Outliers

3.6.1. Missing Data

Missing data can have an impact upon the interpretation of the trial results. In general, values for missing data will not be imputed unless methods for handling missing data are specified. The handling of missing or incomplete dates is described in Section 7.1.5.2 for AE onset, in Section 6.3 for efficacy, in Section 7.4 for prior and concomitant medications, and in Section 7.1.5.2 for missing last dose date.

Values for missing safety laboratory data will not be imputed; however, a missing Baseline/Day 1 result will be replaced with a screening result, if available. If no pre-treatment safety laboratory value is available, the Baseline/Day 1 value will be assumed to be normal (ie, no grade) in the summary of graded laboratory abnormalities. Values for missing vital signs data will not be

imputed; however, a missing Baseline/Day 1 result will be replaced with a screening result, if available.

- If safety laboratory results for a subject are missing for any reason at a time point, the subject will be excluded from the calculation of summary statistics for that time point. If the subject is missing a pre-dose value, then the subject will be excluded from the calculation of summary statistics for the pre-dose value and the change from pre-dose values.

SAS code to calculate the LSS score and handle missing data are provided in [Appendix 6](#).

3.6.2. Outliers

Outliers will be identified during the data management and data analysis process. All data will be included in the data analysis.

